## 6.5      Special safety

### 6.5.1    Hyperglycemia

Hyperglycemia is known to be associated with the treatment of somatostatin analogues. Clinical studies of pasireotide in healthy volunteers and in patients with Cushing's disease, acromegaly or carcinoid syndrome have reported transient, asymptomatic increases in fasting and postprandial glucose levels. Two clinical studies have been conducted [SOM230B2216] and [SOM230B2124] in healthy volunteers to further understand the mechanism of pasireotide-induced hyperglycemia and to evaluate the potential clinical utility of anti-diabetes agents in the management of pasireotide-induced hyperglycemia. Data from [SOM230B2216] study indicate that pasireotide decreases insulin secretion, particularly in the postprandial period, as well as the GLP-1/GIP secretion. Results from [SOM230B2124] study suggest that the incretin-based therapies (GLP-1 analogues and DPP-4 inhibitors) may have the best potential to manage the hyperglycemia associated with pasireotide. Some patients in [SOM230B2305] required insulin to treat their hyperglycemia.

### 6.5.2    Self-monitoring of blood glucose

The principal investigator is to educate the patient on the signs and symptoms of hyperglycemia. Patients must monitor their fasting blood glucose by finger stick at home at least 3 times per week for the first 4-week treatment with pasireotide or when the dose of pasireotide is increased. If a patient does not have any fasting values above 100mg/dL, monitoring can be decreased to at least 2 times per week from week 4 to week 12 and 1 time every week for the rest of the study. If glucose values remain normal (below 100mg/dL), monitoring is at the investigator's discretion during the extension phase (where it is applicable). If any values are observed above 100mg/dL, the guidelines in Figure 6-1 are to be followed. These guidelines are based on the current recommendations from the 2012 ADA and EASD aiming at a glycemic treatment goal of FPG < 130mg/dL (<7.2mmol/L). Appropriate actions such as initiation of anti-hyperglycemic therapy (and referral to diabetes specialist) are to be taken by the investigator as outlined on Figure 6-1. If fasting blood glucose values dictate initiation of anti-hyperglycemic treatment (i.e. confirmed > 130mg/dL by self-monitoring), a fasting plasma glucose sample using the central laboratory is to be

collected prior to initiation of anti-hyperglycemic treatment; however, treatment may be initiated using local laboratory results.

[figure not shown]
It is recommended that the patients be encouraged to keep a diary for their blood glucose for appropriate management throughout the study and present the collected data to their physician/diabetes specialist for evaluation. These data will not be collected by the sponsor.

In addition to self-monitoring, fasting plasma glucose and HbA1c will be collected at study visits per [Table 7-1](#) to [Table 7-4](#). Close and frequent monitoring of blood glucose is needed during pasireotide treatment. Intervention for hyperglycemia is to be implemented in any patient meeting any of the following criteria: FPG > 130mg/dL or HbA1c  $\geq$  6.5%.

Patients with FPG > 160mg/dL or HbA1c > 7.5% despite adjustment of antidiabetic therapy should be referred to a diabetes specialist (or earlier per investigator's judgment).

As outlined in [Table 6-4](#) patients with grade 3 hyperglycemia (FPG value > 250mg/dL; >13.9 mmol/L) at any point in the study should have the dose of pasireotide decreased. Patients who in spite of appropriate therapeutic interventions and despite dose reduction of study drug develop uncontrolled diabetes mellitus and/or consistently high blood glucose values: FPG  $\geq$  240mg/fdL (13.3 mmol/L) or HbA1c value  $\geq$  10% will require study treatment discontinuation.

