Patients who had a baseline mUFC between 1.5 to 5 x ULN showed a greater response rate than patients with a baseline mUFC > 5x ULN (27.2% vs. 8.2%, respectively). Uncontrolled patients (those who did not normalize UFC and had less than 50% reduction from baseline in UFC) could be identified early in the treatment course with a high degree of certainty. Approximately 90% of patients with uncontrolled mUFC at both Months 1 and 2 were also uncontrolled at Months 6 and 12.

Pasireotide was well-tolerated. The majority of AEs were consistent with the known adverse drug reactions of Somatostatin Analogs (SSAs). The most common AEs (incidence  $\geq 10\%$ ) were diarrhea, nausea, abdominal pain, cholelithiasis, hyperglycemia, diabetes mellitus, fatigue and glycosylated hemoglobin increased. Hyperglycemia-related AEs appeared to be the most significant safety concern in terms of frequency of occurrence as well as overall clinical impact (i.e. overall increase in HbA1c of  $\sim 1.5\%$  for both dose groups at 6 and 12 months). Hyperglycemia was managed with the addition or adjustment in oral antidiabetic treatment or in some cases the addition of insulin. Patients who had pre-existing diabetes had a higher degree of hyperglycemia. As expected in successful therapies for hypercortisolism, AEs related to cortisol withdrawal (hypocortisolism) were reported in 13 (8.0%) patients, for which a dose decrease resulted in effective management of the AE.

Overall, pasireotide demonstrated a favorable benefit/risk profile in Cushing's disease. Importantly, patients that are relatively poor responders to pasireotide can be identified early

[figure not shown]
(i.e. after two months of treatment) with a high degree of certainty, thereby giving the option of prompt discontinuation of patients not likely to derive benefit from this drug.

Preliminary data (Feelders 2010) indicate synergic effect between pasireotide and cabergoline in increasing the biochemical control rate in patients with CD. When cabergoline was added to pasireotide in a proof of concept study, UFC normalization increased from 29% to 53%. These preliminary data make cabergoline the best partner for pasireotide in increasing biochemical control rate.

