**Table 6-4 Guidelines for treatment of patients experiencing adverse events**

Patients	Adverse Event	Action
All	AE grade $\leq$ 2 (mild to moderate)	No drug adjustments
	AE grade $\geq$ 3 (severe to life-threatening) and judged as pasireotide-related	Reduce dose of by 0.3mg bid. If AE improves to grade $\leq$ 2 within 1 week, increase dose by 0.3mg bid. If AE recurs at grade $\geq$ 3, reduce dose by 0.3mg bid again and remain at lower dose. If AE does not improve to grade $\leq$ 2 within 1 week on lower dose, reduce dose by 0.3mg bid again if possible. If AE does not improve to grade $\leq$ 2 within 1 week on 0.3mg bid patient should be discontinued from study treatment
	AE grade $\geq$ 3 (severe to life-threatening) and judged as cabergoline-related	Reduce dose from daily schedule to every other day schedule. If AE improves to grade $\leq$ 2 within 1 week, increase dose to daily schedule. If AE recurs at grade $\geq$ 3, reduce dose every other day schedule again and remain at that schedule. If AE does not improve to grade $\leq$ 2 within 1 week on the every other day schedule, patient should be discontinued from study treatment
	All patients	For patients experiencing hyperglycemia, the dose should be reduced if severity grade 3 or greater persists despite appropriate management. If the hyperglycemia is considered to be life-threatening, the patient should be withdrawn from study treatment regardless of anti-diabetes treatment
	AE grade 3 – All patients	NCI-CTCAE v4.03 grades diabetes that is treated with insulin as a grade 3. However, diabetes grade 3 will require a study drug dose reduction only in cases of uncontrolled hyperglycemia despite appropriate management. Patients who despite appropriate therapeutic interventions and dose reduction of study drug, develop uncontrolled diabetes and/or consistently high blood glucose values: FPG $\geq$ 240mg/fdL (13.3 mmol/L) or HbA1c value $\geq$ 10% will require study treatment discontinuation
	Hypocortisolism	If a patient shows high sensitivity to pasireotide 0.6 mg bid resulting in cortisol values $<$ LLN and/or signs/symptoms consistent with the diagnosis of hypocortisolism, the dose of pasireotide can be decreased to 0.3 mg bid. Despite the dose reduction, some patients may still present with cortisol values $<$ LLN and/or signs/symptoms consistent with hypocortisolism; in this case the dose of pasireotide can be further reduced to 0.3 mg qd in order to achieve and maintain normal cortisol levels.

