#### **7.1.2.1 Criteria for premature patient withdrawal**

Patients **may** voluntarily withdraw from the study or be dropped from it at the discretion of the investigator at any time.

Patients **must** be withdrawn from the study if any of the following occurs:

1. Patients experiencing unacceptable drug-related toxicity (as described in [Table 6-1](#))
2. Uncontrolled diabetes mellitus (DM), consistently high capillary glucose values in excess of 275 mg/dL (15.5 mmol/L), FPG  $\geq$  240 mg/dL (13.3 mmol/L) or HbA1c value  $\geq$  10 % despite prior appropriate management and prior dose adjustment of the study drug,
3. Patients experiencing adverse events in QTc:
  - a confirmed QTcF  $>$  480 msec and discontinuation recommended by a cardiologist, or
  - Mean QTcF  $>$  500 msec measured by triplicate ECGs and confirmed by a cardiologist
  - Significant arrhythmia findings from Holter monitoring such as:
    - a. Any ventricular or supra-ventricular tachyarrhythmia associated with symptoms of hemodynamic compromise
    - b. Sustained ventricular tachycardia ( $>$ 30 sec) irrespective of symptoms
    - c. Recurrent non-sustained VT ( $\geq$  3 beats) during any 24-hour monitoring period
    - d. Torsades de Pointes (TdP)
    - e. Cardiac arrest
    - f. Pause  $>$ 5 seconds
    - g. Second or third degree AV block
  - New occurrence of clinically significant/symptomatic bradycardia, or
  - Increased risk of QT prolongation by use of QT prolonging medication, or
  - Hypokalemia ( $<$ 3.5 mmol/L) or hypomagnesaemia ( $<$ 0.7 mmol/L) confirmed by repeat testing that is either a new finding or accompanied by vomiting or diarrhea and not corrected by treatment.

- Evidence of hypoadrenalinism: defined as an early morning (between 8 and 10 am) serum cortisol < 3 µg/dL and a UFC measurement < LLN or symptoms suggestive of hypoadrenalinism (e.g. postural hypotension, nausea, and abdominal pain) in association with a UFC measurement < LLN, which persist after drug dose adjustment
- Lack of efficacy: consistently elevated UFC level and lack of clinical benefit after  $\geq 3$  months treatment
- Pregnancy
- Patient experiencing
  - a. ALT or AST  $> 3 \times$  ULN and Total Bilirubin  $\geq 2 \times$  ULN and ALP  $< 2 \times$  ULN
  - b. ALT or AST  $> 5 \times$  ULN  $\leq 8 \times$  ULN persistent for more than 2 weeks
  - c. ALT or AST  $> 8 \times$  ULN

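### Section 6.5.2 drops Table 6-4's manage-first condition for grade 3 hyperglycaemia, the table does not say which of its rows governs, and one glucose limit in 7.1.2.1 is mis-converted

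*Protocol*

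**What the plan says.** Three places in the protocol bear on what to do with pasireotide when glucose reaches grade 3.

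- **Section 6.5.2** presents its rule as coming from Table 6-4. It says that those who have "grade 3 hyperglycemia (FPG value > 250mg/dL; >13.9 mmol/L) at any point in the study should have the dose of pasireotide decreased". It sets no condition about earlier treatment, persistence or drug-relatedness.
- **Table 6-4, hyperglycaemia row:** "the dose should be reduced if severity grade 3 or greater persists despite appropriate management". **Grade 3 diabetes row:** "diabetes grade 3 will require a study drug dose reduction only in cases of uncontrolled hyperglycemia despite appropriate management".
- **Table 6-4, general row**, for events of grade 3 or higher judged pasireotide-related: reduce by 0.3 mg bid, and step back up if the event improves to grade 2 or lower within 1 week. **Section 6.6** likewise asks for reduction or withdrawal when such toxicity is directly attributable to pasireotide. Neither has a persistence condition.

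Glucose treatment itself starts much lower. Section 6.5.2 describes its guidance as "aiming at a glycemic treatment goal of FPG < 130mg/dL (<7.2mmol/L") and says "Intervention for hyperglycemia is to be implemented in any patient meeting any of the following criteria: FPG > 130mg/dL" (or an HbA1c criterion).

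On mandatory withdrawal, Section 7.1.2.1 lists "consistently high capillary glucose values in excess of 275 mg/dL (15.5 mmol/L") and, in the same item, an FPG limit of "240 mg/dL (13.3 mmol/L").

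**The concern.** Section 6.5.2 says it restates the table, but the rule it gives has a different trigger from the two rows written for this event. An investigator working from 6.5.2 alone would lower pasireotide at any grade 3 value. One who turns to the hyperglycaemia row would treat the glucose first and reduce only if grade 3 persists. One who applies the general row would reduce if the event is judged related. The table does not rank its rows.

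What is at stake is consistent dosing across sites, and the safety summaries that depend on dosing. Protocol Section 10.3.1.5 measures tolerability by dose reduction or interruption due to an adverse event. SAP Section 6.6.1 tabulates events requiring dose adjustment. Hyperglycaemia is an event of special interest under Protocol Section 8.1.2. If sites follow different texts, these counts partly reflect which text was read.

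The unit error is a separate matter. It sits in a mandatory-withdrawal criterion of an international study, where some sites may work in mg/dL and others in mmol/L.

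**Working it through.** **Dosing rule: the texts applied to three situations**

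| Situation | Section 6.5.2 | Table 6-4 hyperglycaemia row | Table 6-4 general row |
|---|---|---|---|
| First FPG of 260 mg/dL, no antidiabetic treatment started or adjusted | Reduce | Treat first, do not yet reduce | Reduce if judged pasireotide-related |
| Transient FPG of 260 mg/dL during ongoing treatment, then settling | Reduce | Do not reduce, because it has not persisted | Reduce if judged related, then re-escalate if improved within 1 week |
| FPG stays above 250 mg/dL despite appropriate management | Reduce | Reduce | Reduce if judged related |

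The value of 260 mg/dL is illustrative: 260/18.016 = 14.4 mmol/L, above the 13.9 mmol/L limit. Section 6.5.2 and the hyperglycaemia row disagree in the first two situations and agree in the third. The grade 3 diabetes row also withholds a reduction while appropriate management is controlling the glucose.

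**Size of the dose step.** The hyperglycaemia row gives no step. Assuming the general row's 0.3 mg bid:

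- from 0.6 mg bid: 0.3/0.6 = 50%
- from 0.9 mg bid: 0.3/0.9 = 33%

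**Frequency.** The value of 260 mg/dL is 260/130 = 2.0 times the level at which treatment is already required. The documents give no count of patients who reach grade 3 untreated or only transiently, so no rate can be stated.

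**Unit conversion.** The formula is mmol/L = (mg/dL)/k. Assuming a glucose molar mass of about 180.16 g/mol, k = 18.016.

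| Limit | Stated mmol/L | mg/dL ÷ 18.016 | k implied by the stated pair, allowing for rounding | Agrees |
|---|---|---|---|---|
| 130 mg/dL (6.5.2) | 7.2 | 7.22 | 17.93 to 18.18 | yes |
| 240 mg/dL (6.5.2, Table 6-4, 7.1.2.1) | 13.3 | 13.32 | 17.98 to 18.11 | yes |
| 250 mg/dL (6.5.2) | 13.9 | 13.88 | 17.92 to 18.05 | yes |
| 275 mg/dL (7.1.2.1) | 15.5 | 15.26 | 17.69 to 17.80 | no |

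The first three pairs share the range k = 17.98 to 18.05, which the fourth does not reach. The mismatch therefore shows from the protocol's own figures, whatever value of k is assumed. Over that range 275 mg/dL is 15.24 to 15.30 mmol/L. In the other direction, 15.5 × 18.016 = 279.2 mg/dL, a gap of 279.2 − 275 = 4.2 mg/dL.

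**The case against.** The strongest reply is that Table 6-4 does support 6.5.2, through its general row. Section 6.5.1 treats hyperglycaemia as a known effect of this drug class, so a grade 3 value will often be judged related, and the general row and Section 6.6 then call for action without waiting for persistence. Part of this stands: the table leaves precedence open and is itself part of the problem. It does not make 6.5.2 a faithful paraphrase. Section 6.5.2 has no relatedness condition and no re-escalation step. The word *only* in the diabetes row signals an intended exception to the usual grade 3 handling.

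A second reply is that the stricter wording in 6.5.2 may be what the sponsor wanted. Treating glucose and lowering pasireotide can be done together. The phase III account in Section 1.2.1.2 ("Hyperglycemia was managed with the addition or adjustment in oral antidiabetic treatment or in some cases the addition of insulin") describes experience and is not a dosing rule. Figure 6-1, which governs the response to raised self-monitored values, is not available here. This stands as a limit on certainty. A reader might infer that 6.5.2 is simply the wrong text, but the documents do not settle that. They show only that 6.5.2 defers to a table whose event-specific rows say something else.

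A third reply is that the practical conflict is small. The sentence points the investigator to the table. Section 6.6 calls the table a guideline and asks that deviations be agreed with the sponsor. Treatment starts above 130 mg/dL, with specialist referral above 160 mg/dL despite adjusted therapy. This supports a minor rating. It does not remove the transient-value case, which can arise while treatment is under way.

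**Conclusion.** The point holds as a minor inconsistency in a safety dosing rule. Section 6.5.2 omits a condition carried by the two rows of Table 6-4 that deal with this event, and the table does not say whether those rows displace its general row. The actions differ for a first grade 3 value before management and for a transient one during it. They coincide between 6.5.2 and the hyperglycaemia row once grade 3 persists despite management. Where they differ, the amount at issue is one dose step, 33% or 50% if the general 0.3 mg bid step applies. Aligning 6.5.2 to the table is the natural repair, subject to clinical confirmation.

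Two further inferences are not supported. A reader might conclude that the primary endpoint is compromised because pasireotide dose can influence mUFC. The documents give nothing from which to size such an effect, and the week 35 analysis rules are untouched. A reader might also doubt the withdrawal and discontinuation limits generally. The FPG limit of 240 mg/dL converts correctly, and it is not in conflict with the 250 mg/dL reduction threshold, because it applies only after treatment and dose reduction have failed.

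The 275 mg/dL pairing is a plain numerical slip of about 4 mg/dL. Its practical effect is small: the criterion needs consistently high values after management and dose adjustment, and the lower FPG limit is an alternative trigger in the same item.

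**What to change.** 1. In Section 6.5.2, state that, as set out in Table 6-4, pasireotide should be decreased if FPG >250 mg/dL (13.9 mmol/L) persists despite appropriate antidiabetic management.
2. In Table 6-4, add one sentence saying that the hyperglycaemia and diabetes rows apply in place of the general row for grade 3 or higher events.
3. Before making either change, have the sponsor's clinical team confirm that managing first is the intended rule and that Figure 6-1 agrees. If immediate reduction is intended instead, the two table rows are what should change.
4. In Section 7.1.2.1, change 15.5 to 15.3 mmol/L.

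The cost is a few words, one sentence and one number, which can go into any protocol amendment. Visits, data collection and analysis do not change.

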**Figure 6-1 Fasting Self-Monitoring Blood Glucose guidelines**

[figure not shown]

### 6.5.3 QT prolongation

If at any visit a QTcF>500 msec is observed, triplicate ECGs, each 2-3 min apart need to be taken approximately 1 hour after the initial ECG. The mean QTcF from the triplicate ECGs will be determined. If the mean QTcF is >500msec, the patient has to discontinue the study medication until a cardiologist has re-evaluated the ECG. The re-evaluation is required to be done as soon as practical but within 7 days of the initial finding of abnormal ECG. If the cardiologist confirms a mean QTcF >500msec, the patient will be withdrawn from the study. Otherwise and if the cardiologist confirms that at least one ECG shows QTcF >480msec, the cardiac assessments described for a confirmed QTcF >480msec are to be followed.

If at any visit a 480 msec > QTcF  $\leq$  500 msec is observed for the first time for a patient at a given dose level, the following steps are to be taken (as described in [Figure 6-2](#)):

- A cardiology consultation must be sought as soon as practical but within 7 days of the initial finding of abnormal ECG and the cardiologist is to re-evaluate the ECG
  - If a QTcF >480msec is NOT confirmed, no further action is to be taken
  - If a QTcF > 480msec is confirmed, a cardiologist must perform a thorough examination (such as reviewing baseline ECG, concurrent medications and performing a cardiovascular examination (including at least a cardiac auscultation) to assess the patient for cardiovascular risk factors).
    - If based upon the assessment by the cardiologist, the investigator considers that there is an acute cardiovascular safety risk and that the patient should not continue with study medication, the patient is to be discontinued immediately (discontinuation criteria to be followed).
    - If following the examination by the cardiologist, the investigator considers that there is not an acute cardiovascular safety risk and that the patient could continue to receive study medication, a 24-hr HolterECG is to be recorded as soon as practical but within 7 days after the initial finding of abnormal ECG. The Holter ECG is to be started 30 minutes prior to an injection of study medication.
    - The results of the ECGs, cardiac examination, Holter ECG and the recommendations by the cardiologist are to be evaluated by the Investigator to determine whether the patient should continue in the trial or not (discontinuation criteria to be followed)

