## 5.2 Exclusion criteria

Patients must not meet any of the following exclusion criteria at screening:

1. Patients with compression of the optic chiasm causing any visual field defect that requires surgical intervention
2. Diabetic patients with poor glycemic control as evidenced by HbA1c >8%
3. Patients with risk factors for torsade de pointes, i.e. patients with a baseline QTcF >450 ms in males, and > 460 ms in females. hypokalemia, hypomagnesaemia, uncontrolled hypothyroidism, family history of long QT syndrome, or concomitant medications known to prolong QT interval
4. Patients with clinically significant valvular disease
5. Patients with Cushing's syndrome due to ectopic ACTH secretion
6. Patients with hypercortisolism secondary to adrenal tumors or nodular (primary) bilateral adrenal hyperplasia
7. Patients who have a known inherited syndrome as the cause for hormone over-secretion (i.e. Carney Complex, McCune-Albright syndrome, MEN-1)
8. Patients who are hypothyroid and not on adequate replacement therapy
9. Patients with symptomatic cholelithiasis
10. Patients who have congestive heart failure (NYHA Class III or IV), unstable angina, sustained ventricular tachycardia, clinically significant bradycardia, advanced heart block, history of acute MI less than one year prior to study entry or clinically significant impairment in cardiovascular function
11. Patients with liver disease such as cirrhosis, chronic active hepatitis, or chronic persistent hepatitis, or patients with ALT/AST > 2 X ULN, serum bilirubin >2.0 X ULN
12. Patients with serum creatinine >2.0 X ULN
13. Patients with WBC <3 X 10^9/L; Hb 90% < LLN; PLT <100 X 10^9/L
14. Patients who have a history of alcohol or drug abuse in the 6 month period prior to receiving pasireotide
15. Patients who have participated in any clinical investigation with an investigational drug within 1 month prior to dosing
16. Patients with active malignant disease within the last five years (with the exception of basal cell carcinoma or carcinoma in situ of the cervix)
17. Patients with the presence of active or suspected acute or chronic uncontrolled infection
18. Patients with a history of non-compliance to medical regimens or who are considered potentially unreliable or will be unable to complete the entire study
19. Patients with presence of Hepatitis B surface antigen (HbsAg)
20. Patients with presence of Hepatitis C antibody test (anti-HCV)

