**Figure 6-2 QT Prolongation monitoring flow chart**

#### 6.5.4 Hepatic Safety Management

Patients who develop increased transaminase and/or total bilirubin ( $> 2.0 \times \text{ULN}$ ) levels, should be monitored with a second liver function evaluation for confirmation. If confirmed, liver function should be frequently monitored until values return to pre-treatment levels.

If any of the criteria below are observed at any scheduled or unscheduled visit the sponsor should be notified immediately and the Hepatic Safety evaluation, described below, should be performed preferably within 48- hours of awareness of the abnormality:

Patient experiencing

- ALT or AST  $> 3 \times$  ULN and total bilirubin  $\geq 2 \times$  ULN
- ALT or AST  $> 5 \times$  ULN
- total bilirubin  $> 2.0 \times$  ULN

The following should be performed immediately within 72 hours of awareness of the abnormality:

[figure not shown]
- Perform liver-directed medical history and physical examination (i.e. assess occupational hazards, concomitant medications including OTC meds, inter-current illness, etc.)
- Liver function tests: ALT, AST, total bilirubin, (fractionate to direct/indirect bilirubin if total bilirubin is  $> 2.0 \times$  ULN), Albumin, PT, INR, ALP, and GGT.
- Perform hepatitis screen: anti-HAV, IgM (to confirm acute Hepatitis A), HbsAg, Anti-HBc, anti-HCV (if positive, PCR viral load should be assessed), Anti-HEV, ANA antibodies, anti-smooth muscle anti-bodies, CMV and EBV
- Perform abdominal ultrasound (liver and biliary tree)

[figure not shown]
Liver function tests (LFTs) should be monitored every 3-4 days until resolution or return to baseline status.

Patients should be managed according to the LFT algorithm [Figure 6-3](#). Patients may need to be discontinued if the abnormal liver function criteria are met upon LFT retesting (See discontinuation criteria [Section 7.1.2.1](#)). Progress reports of the event should be maintained until resolution or stabilization (i.e. no further elevation after 2 consecutive assessments).

If any of these criteria are met and not confirmed by repeat testing, and the event is considered to be an adverse event by the investigator, the event must be recorded on the Adverse Event eCRF page; if the event is deemed serious by the investigator, then proceed with completing the SAE form. In addition, any significant findings from the physical examination should be recorded on the Adverse Event eCRF page.

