No dose reductions are required in case of a QT prolongation but guidelines for QT monitoring and discontinuation criteria outlined in Section 6.5.3		

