#### 7.2.2.5.9 Cardiac assessments

##### Electrocardiogram (ECG)

A 12-lead ECG and a rhythm strip will be performed at the sites at visits indicated in [Table 7-1](#) and [Table 7-2](#). All ECGs should include all 12 standard leads and a Lead II rhythm strip of at least a 10- second duration. The ECGs will be performed on the machine(s) provided for the study by the central reader and are sent to the central reader for evaluation. To ensure consistency throughout all participating sites, the ECGs should be performed and processed following the guidelines from the central reading facility, which will be distributed to the sites. A Holter ECG will be required in case of a confirmed QTcF  $> 480$ msec (described in [Section 6.5.3](#)).

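### Protocol 6.5.3 prints the lower bound of the QT work-up trigger with its sign reversed, so as written it omits QTcF readings above 480 and up to 500 msec; wrong as written, low practical severity

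*Protocol*

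**What the plan says.** Protocol Section 6.5.3 has two tiers. A QTcF above 500 msec leads to triplicate ECGs and, if the mean stays above 500 msec, to stopping study drug until a cardiologist has re-read the tracing. If the cardiologist does not confirm a mean above 500 msec but finds at least one ECG above 480 msec, "the cardiac assessments described for a confirmed QTcF >480msec are to be followed".

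The lower tier has its own sentence, beginning "If at any visit a 480 msec > QTcF". It continues with an upper limit of 500 msec, inclusive, applies to the first such reading for a patient at a given dose level, and refers to Figure 6-2. The steps under it are a cardiology consultation within 7 days, a re-read of the ECG and, if the finding is confirmed, an examination and possibly a 24-hour Holter recording. The re-read step says "If a QTcF >480msec is NOT confirmed, no further action is to be taken".

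Other sections depend on this one:

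- Table 6-4: "No dose reductions are required in case of a QT prolongation but guidelines for QT monitoring and discontinuation criteria outlined in" Section 6.5.3.
- Section 7.1.2.1 withdraws a patient with a confirmed QTcF above "480 msec and discontinuation recommended by a cardiologist".
- Section 7.2.2.5.9: "A Holter ECG will be required in case of a confirmed QTcF" above 480 msec, with a pointer back to 6.5.3.

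**The concern.** The sentence that opens the lower tier carries a lower bound facing the wrong way. Read as printed, it describes patients below 480 msec, not those above it.

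The later steps hang on this sentence. In the text of 6.5.3 it is the only direct way into the work-up for a reading of 481 to 500 msec, because the other route needs an initial reading above 500 msec. The Holter rule and the withdrawal criterion both presuppose a confirmed reading, and confirmation is the step that this sentence starts. Table 6-4 asks for no dose reduction for QT prolongation and relies on 6.5.3 instead.

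QT is a recognised issue for this drug. Section 1.2.1.2 reports a peak placebo-subtracted QTcF change of 17.5 ms at a supra-therapeutic dose, and Section 8.1.2 lists QTc prolongation among events that may need targeted follow-up. Section 12 allows no authorised deviations, so a site should not have to set aside the literal wording to do what was meant.

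**Working it through.** The check is logical; no sample size, power or event count enters, and the plan gives no figure to reproduce.

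**1. The condition as printed.** Let q be QTcF in msec. The printed trigger is (480 > q) and (q ≤ 500). Any q below 480 is also at most 500, so the second half does no work and the condition reduces to q < 480.

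**2. The condition with the first sign turned.** (480 < q) and (q ≤ 500), that is, above 480 and up to 500.

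**3. Both conditions at the values that matter.**

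| q (msec) | Printed trigger | Corrected trigger | Path for readings above 500 |
|---|---|---|---|
| 450 | met | not met | not met |
| 460 | met | not met | not met |
| 480 | not met | not met | not met |
| 481 | not met | met | not met |
| 500 | not met | met | not met |
| 501 | not met | not met | met |

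The rows for 450 and 460 are the eligibility limits in exclusion criterion 3, which rules out "patients with a baseline QTcF >450 ms in males, and > 460 ms in females". On treatment, values at those levels would satisfy the printed trigger. The rows for 481 and 500 bound the band that is lost, which is 500 − 480 = 20 msec wide. The corrected trigger meets the path above 500 msec with no gap and no overlap.

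**4. The threshold used elsewhere.**

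| Place | Threshold | Fits the printed trigger? |
|---|---|---|
| 6.5.3, re-read and confirmation steps | above 480 | no |
| 6.5.3, paragraph on readings above 500 | above 480, confirmed | no |
| 7.1.2.1, withdrawal | above 480, confirmed | no |
| 7.2.2.5.9, Holter | above 480, confirmed | no |

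A trigger of q < 480 followed by a step asking whether a value above 480 is confirmed makes no sense as a sequence. A trigger of 480 < q ≤ 500 does. Four operative statements agree on above 480, and the opening sentence alone differs.

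**The case against.** The strongest reply is that the section corrects itself. The bullets under the sentence speak of an abnormal ECG and ask about values above 480 msec, the paragraph above does the same, and the upper limit of 500 would be pointless under the literal reading. A site would very probably act on the intended band. This stands, and it is why practical severity is low.

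Second, the sentence refers to a flow chart that is not in the text reviewed; only its caption, "Figure 6-2 QT Prolongation monitoring flow chart", is visible. If the chart shows the right band, sites had the correct algorithm in front of them. That also stands, but text and figure would then disagree and the text would still need correcting.

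Third, the sign could have been misread from the PDF. There is some reason for caution: the highest baseline mUFC category in Protocol 10.2.4 appears without the greater-than sign that SAP 6.5.1 prints for it. That is a missing sign rather than a reversed one, and the other QTcF thresholds in 6.5.3 read consistently. A misreading is not excluded; a look at the source page would settle it.

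Two stronger readings are tempting and are not supported:

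- A reader might infer that every eligible patient's baseline ECG would call for a cardiology consultation, since the eligibility limits lie below 480 msec. The trigger is tied to a dose level, and Table 7-1 takes the ECG before the pasireotide dose. A patient not yet on pasireotide is at no dose level at baseline. At most the point could be argued for patients already on pasireotide at entry, whom Section 10.5 assumes to number no more than 6 of 64. The literal consequence is safe to state only for readings on treatment.
- A reader might infer that SAP 6.6.4 is contradicted, because it uses above 480 ms. That is one of several descriptive categories for tabulation. It fits the intended threshold but triggers no work-up, so nothing in the SAP conflicts with the Protocol sentence.

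**Conclusion.** The trigger in Protocol 6.5.3 is wrong as written. Literally it means QTcF below 480 msec: normal ECGs on treatment would call for a cardiology consultation, and readings of 481 to 500 msec would not. This conflicts with the above-480 threshold in the section's own sub-bullets, in its paragraph on readings above 500 msec, in 7.1.2.1 and in 7.2.2.5.9. It is a drafting error in an operative safety rule, not a dispute about where the threshold should lie.

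Practical severity is low because the intent can be read from the lines that follow. The documents give no ground for saying that a patient was missed or mishandled. The primary endpoint, the sample size and the SAP's QT tabulations are untouched. The conclusion assumes that the sign in the reviewed text is the sign in the source document, and it makes no assumption about what Figure 6-2 shows.

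**What to change.** In Protocol 6.5.3, write the trigger as 480 msec < QTcF ≤ 500 msec. Check the source page to confirm the printed sign, and check that Figure 6-2 gives the same band, correcting it if it does not. The SAP needs no change.

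The cost is one symbol and one figure check, with no added visits, procedures or patients. It can go into any amendment made for another reason; Amendment 1 already corrected a figure reference in this same section.
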